## **C.4. Study Visits**

**Visit # 1:** During this visit, the PI will explain the study objectives, study protocol, and sequences of events and answer any remaining questions that the subject may have about the study. If after such conversation with the PI, the subject is still willing to freely participate in the study, then he/she will sign the informed consent prior to the beginning of the screening process. Specifically, subjects will obtain overview of the study and the PI will complete endothelial function assessment using EndoPat2000 device. Subjects with RHI of 2.0 or less will be eligible and will be asked to provide blood sample for triglyceride measurement. First visit will end with the collection of blood specimen and subjects will be told that the coordinator will notify them via telephone of the results for further eligibility. Only subjects with triglycerides between 150 and 400 mg/dl will be eligible to be invited to the second study visit.

**Visit # 2:** Eligible subjects identified during visit # 1 will be asked to the CCI fasting but will be allowed to take their usual morning medications. Subjects will be instructed to start fasting at 8PM of the night before the study visit. Pregnancy test will be done to rule out pregnancy among pre-menopausal women without history of surgical sterilization. For subjects randomized to Vascepa, women who can become pregnant during the study will be asked to use a contraceptive method (i.e., hormone, intrauterine device, barrier, or abstinence) during the study and six months after the final visit. During the second visit, we will collect baseline blood samples (20 ml) for measurement of biomarkers (hsCRP, ET-1, and oxLDL); other relevant biomarkers (i.e., TNF $\alpha$ , NTproBNP, apoC3, apoA5, galectin 3, free fatty acids, relevant single nucleotide polymorphisms, and fatty acids will be measured at a later time upon securing new funding on stored blood specimens). Resting blood pressure and pulse will be measured (2x) after 15 minutes of rest and information on age, sex, race, education, height, weight will be collected. Subjects will also complete a Willett food frequency questionnaire to assess their baseline diet. Digital pulse amplitude measurements (see C.6. below) will be done. A dedicated research assistant (RA) will discuss the randomization scheme provided by the statistician with the subjects. The RA will not be blinded to the treatment assignment. Otherwise, PI, study coordinator, statistician, and other staff at the lab measuring biomarkers will all be blinded. Subjects randomized to Vascepa will know that they are taking the drug containing omega-3, since the drug is not disguised and there is no placebo (open label trial). The RA will advise subjects not randomized to Vascepa (control subjects) to continue their usual habits. Each subject randomized to EPA will receive a 12-week supply of study EPA from the BWH pharmacy with the instructions to take 4 g/d. Each subject will receive a study diary to record potential adverse effects during the next 12 weeks. Enrolled subjects will be contacted by telephone once a month by the coordinator to query about potential adverse effects and remind them of the upcoming final visit.

**Visit # 3:** Subjects will be invited to come to the CCI fasting (starting from 8PM of the night before the visit) during the last visit, which will be 12 weeks after the second visit. Subjects will be allowed to take their morning medications prior to the visit. During the last visit, we will also complete count of any leftover pills among subjects randomized to EPA and repeat all study procedures conducted during the second visit.

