#### A. Inclusion criteria

- Age 30-75 years
- Hypertriglyceridemia (150-400 mg/dl)
- Statin use for at least six months at the time of screening
- Type 2 diabetes treated with diet and/or oral hypoglycemic agents diagnosed 1+ year from first visit
- Ability to provide informed consent and provide blood samples
- Willingness to abstain from fish oil, EPA, over the counter niacin, and other omega-3 fatty acid supplements during the study period (12 weeks)
- Ability to travel to the study site at Brigham and Women's Hospital for 3 study visits
- RHI of  $\leq 2.0$

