#### B. Exclusion criteria

- Eating disorder or heavy drinkers (>2 standard drinks/d: a drink= 1.5 oz liquor, 4oz wine, or 12 oz beer)
- Treatment with chronic prescription pharmacotherapy for metabolic or cardiovascular disease management or risk factor modification (e.g., antihypertensive medications) that has not been stable for  $\geq 4$  weeks prior to screening
- Pregnant or lactating women
- Statin use <6 months at the time of screening
- Allergy to EPA, fish oil, shellfish, or other omega-3 fatty acids
- Current use of insulin, cyclophosphamide, estrogen, fibrates, niacin, hormone replacement therapy, testosterone, oral contraceptives, growth hormones, insulin-like growth factor-1, and other systemic steroids.
- Inability to provide informed consent or blood samples
- History or prevalent diagnosis of cancer, asthma, kidney insufficiency, stroke, seizures, allergic disorders, liver disease, or congestive heart failure
- Diagnosis of diabetes < 1 year prior to enrollment

- ❑ Intention to move out of greater Boston area within one year
  - ❑ Current use of omega-3 supplements, fish oil, or  $\geq 2$  servings of fish per week
  - ❑ Bleeding disorder or uncontrolled endocrine (i.e., thyroid) or metabolic disorders
  - ❑ Treatment with blood thinning drugs (i.e. warfarin and clopidogrel)
  - ❑ Major surgical operation 3 months before or after screening
  - ❑ Organ transplantation
  - ❑ Current participation in another trial or plan to do so during the study
  - ❑ Inability to give informed consent or to travel to the study center at Brigham and Women's Hospital
  - ❑ RHI of  $>2.0$
  - ❑ Triglycerides  $<150$  mg/dl or  $>400$  mg/dl
  - ❑ Body mass index of  $40+$  kg/m^2
- 

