## **C.2. Recruitment of Study Subjects**

Upon receiving IRB approval from Brigham and Women's Hospital (BWH), potential participants will be recruited via usual advertisement techniques, including flyers posted on campus, media advertisement, and use of Partners Biobank (a letter co-signed by Partners Biobank PI and [name] with a card and a prepaid return address will be used). Each flyer will contain pertinent information summarizing the study protocol and objectives and contact information for study staff. Interested participants will contact the study coordinator, who will conduct a telephone screening for eligibility. Once a potential study subject has been determined to be eligible via telephone, he/she will be provided with detailed information about the study by the PI/study coordinator. The potential participant will then review the study materials before determining if he/she will voluntarily participate in the study. If yes, he/she will call the investigative team for an appointment for the first visit (screening) at the CCI, Brigham and Women's Hospital, Boston, MA. The goal would be to recruit and enroll 30 people with prevalent DM, triglycerides between 150 and 400 mg/dl, and current statin use. We will build in margin for 10% attrition and recruit 33 subjects overall. Details on inclusion and exclusion criteria are provided in **Table 2**.

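### Visits 2 and 3 combine a fast from 8PM with permission for all usual morning medications, with no exception for oral agents that can cause low glucose: a minor, avoidable safety risk

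*Combined protocol and SAP*

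**What the plan says.** All references are to the combined protocol and SAP.

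- **Population.** Table 2 (A. Inclusion criteria) requires "Type 2 diabetes treated with diet and/or oral hypoglycemic agents diagnosed 1+ year from first visit". Table 2 (B. Exclusion criteria) rules out "Current use of insulin, cyclophosphamide, estrogen, fibrates, niacin" and several hormones, but no class of oral glucose-lowering drug.
- **Visit 2 (C.4).** On the fast: "Subjects will be instructed to start fasting at 8PM of the night before the study visit". On medication, subjects are "asked to the CCI fasting but will be allowed to take their usual morning medications".
- **Visit 3 (C.4).** The same 8PM start applies, and "Subjects will be allowed to take their morning medications prior to the visit".
- **What happens while fasting.** Both visits include a blood draw, resting blood pressure, a food questionnaire and the PAT test. C.6 requires the PAT test to be done fasting.

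The supplied text does not treat glucose-lowering drugs separately from other morning medication on these two days. Nor does it say when the fast ends or when food is offered.

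**The concern.** The trial enrols only people with type 2 diabetes, and some of them may be on tablets whose purpose is to lower glucose. On two mornings the visit rule lets such a subject take that tablet after an overnight fast, travel to the site and go through the procedures without eating. For agents that can cause low glucose, this is the situation in which it is most likely to occur.

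What is at stake is the safety and comfort of those subjects on two visits. The measurements need a fasting subject, but nothing in the plan needs this particular tablet to be taken before them. The exposure is therefore avoidable without giving up the fasting state.

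**Working it through.** The point rests on no sample-size, power or alpha figure, so the check is a side-by-side reading plus simple timing.

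**1. Does the rule permit the combination?**

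| Element | Source | Content |
|---|---|---|
| Who | Table 2, A | Type 2 diabetes on diet and/or oral agents |
| Limit on who | Table 2, B | Insulin users out; no oral glucose-lowering class out |
| Fast | C.4, visits 2 and 3 | From 8PM the evening before |
| Medication | C.4, visits 2 and 3 | Usual morning doses allowed, no exception |
| Fasting procedure | C.6 | PAT test in the fasting state |

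Read together, a subject who follows C.4 exactly may take an oral hypoglycemic agent unfed at both visits. Subjects on diet alone, on agents that do not cause low glucose, or who choose not to take the dose are not affected.

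**2. How long is the fast?** The documents give no visit time. Assume procedures start between 7AM and 11AM. From 8PM to midnight is 4 hours, so the fast lasts 4 + 7 = 11 hours to 4 + 11 = 15 hours at that point.

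**3. How long unfed on site after the tablet?** C.6 gives a rest of at least 20 minutes, a baseline of about 5, an occlusion of 5 and a recording of up to 4:

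20 + 5 + 5 + 4 = about 34 minutes.

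C.4 adds "Resting blood pressure and pulse will be measured (2x) after 15 minutes of rest". If that rest is separate from the PAT rest:

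34 + 15 = about 49 minutes.

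The blood draw and travel come on top, with no stated duration. So may the food questionnaire, which C.4 lists before the PAT test at visit 2 without fixing an order. At visit 3 the research assistant sees each subject before the blinded staff (C.6), which also adds time.

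**4. How many subjects, and how many events?** This cannot be computed. The documents name no oral drug class, give no share of users and give no rate of low glucose. The only bound is the number of mornings: two per affected subject.

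**5. Does moving the dose disturb the primary comparison?** D.1 compares the change in RHI from baseline to post-intervention between arms. If the dose is held at both visit 2 and visit 3, each affected subject is measured before that dose on both occasions. With an unchanged regimen, the within-subject change is like-for-like, as it is now. Screening is different: C.4 states no medication rule for visit 1, so a screening RHI may have been taken after the dose and the visit 2 RHI before it.

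**The case against.** The strongest case against is that this is hardly a defect. Medication is allowed, not required, so no study instruction tells anyone to take a glucose-lowering tablet unfed, and a subject's own clinician may already have advised on fasting mornings. Day-of-visit advice often sits in consent or instruction material, and consent pages are not in our copy. The investigator also explains the sequence of events at visit 1. Insulin is excluded, there are only two such mornings, and both take place at a hospital investigation center.

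All of that stands and keeps the severity low. It does not remove the point: C.4 states a rule without an exception, and a safer wording is available at little cost. If suitable advice exists elsewhere, C.4 should agree with it.

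Two further objections shape the remedy.

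- **Breadth.** Holding every oral glucose-lowering agent would delay doses for subjects whose drug carries no such risk. This is accepted; the exception should cover only agents that can cause low glucose.
- **Measurement condition.** The present rule measures RHI and biomarkers under usual morning therapy, and Table 2 requires metabolic and cardiovascular medication to be stable before screening. Holding a dose changes that condition for the subjects concerned. This is also accepted and has to be disclosed. Because C.3 stratifies on gender and ethnicity only, the number of such subjects may differ between arms; the comparison still rests on within-subject change under the same rule at both visits.

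**Conclusion.** The point holds as a low-severity, optional improvement. C.4 permits an unfed dose of an oral agent that can cause low glucose on up to two mornings per subject, followed by at least about 34 to 49 minutes of procedures plus the blood draw. The size of the risk is unknown.

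This rests on one clinical assumption that the documents do not spell out: some of the oral agents admitted by Table 2 can cause low glucose when taken without food.

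A reader might infer more, and the documents do not support it:

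- *That the protocol directs subjects to take the tablet fasting.* The wording only permits it.
- *That subjects receive no advice.* The finding concerns the wording of C.4; silence there does not show silence in the consent material.
- *That a given number of the 30 randomized subjects is affected.* Any such count would rest on an assumed share of users and would include people who never use the permission.
- *That the trial's results are compromised.* Sample size, power and the primary analysis are untouched.

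**What to change.** In both the visit 2 and visit 3 paragraphs of C.4, replace the general permission with:

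*Subjects may take their usual morning medications except oral glucose-lowering agents that can cause low glucose (as identified by the investigator at visit 1), which they bring and take with food once the fasting blood draw and PAT test are complete.*

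Use the same wording in both arms and at both visits, and offer food at that point. Identification at visit 1 precedes randomization, so it does not touch the blinding. Eligibility already turns on which drugs a subject takes, so the information should be to hand.

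**Cost.** One sentence in each of two paragraphs, and a snack at two visits. For the subjects concerned, one dose is delayed on two mornings by travel, the blood draw and the 34 to 49 minutes above. Their RHI and biomarkers are then measured before rather than after that dose. This is the same at baseline and week 12, but may differ from the condition of the screening RHI; the protocol should say so. Evening doses are unchanged, so the risk is reduced, not removed.

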## Study Protocol and Statistical Analysis Plan

### C.1. Study Design

We will use a randomized single blind controlled trial design to address proposed aims. Specifically, the Center for Clinical Investigation (CCI) at Brigham and Women's Hospital will recruit adults aged 30+ years for participation in this study. In order to be eligible, a participant must be diagnosed with 1) type 2 diabetes at least one year prior to enrollment, 2) have elevated serum triglycerides (150-400 mg/dl), 3) a RHI  $\leq 2.0$ , and 4) be on statin treatment for at least six months at the time of enrollment. Additional eligibility criteria include a) ability to travel to the study site at Brigham and Women's Hospital for three study visits, the last two being spaced by 12 weeks, b) ability to provide informed consent, and c) willingness to abstain from fish oil and other forms of omega-3 supplements during the study period. Exclusion criteria include a) current eating disorders, b) pregnancy (using urine test for all premenopausal women of childbearing age without surgical sterilization), c) allergy to EPA or other omega-3 fatty acids, d) inability to provide informed consent, e) history or prevalent diagnosis of cancer, asthma, kidney insufficiency, stroke, or seizures, f) inability to provide blood specimens, g) current use of fish oil, >2 servings of fish per week, or omega-3 fatty acid supplements, and h) intention to move out of greater Boston area within one year. Complete list of inclusion and exclusion criteria is provided in Table 2.

**Table 2.** Inclusion and exclusion criteria

---

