For statistical analysis, we will calculate the pulse amplitude response to hyperemia for each 30-second interval as a ratio of the post-deflation pulse amplitude to the baseline pulse amplitude as described previously. The RHI will be computed by dividing the ratio obtained on the test side (side with blood pressure cuff) over the ratio obtained on the control finger. Since the peak of the RHI has been shown to occur between 90 and 120 seconds after the cuff release, we will use the average of RHIs obtained at 90 and 120 seconds post deflation for analysis. The reproducibility of this technique has been described previously. RHI is correlated with traditional brachial ultrasound and CVD risk factors. Low RHI has been associated with CAD events and improve CAD prediction beyond traditional risk factors.

In order to preserve blinding of key personnel, the PI will complete the assessment of endothelial function and an independent research assistant will share the assignment group with the study subject once all activities of study visit # 2 have been completed and PI and other staff have left the CCI. The RA will instruct the subjects assigned to Vascepa on how to obtain the study drug at the BWH research pharmacy. Furthermore, during the third visit, the RA will see all study subjects before any blinded staff and collect Vascepa bottle with remaining capsules when applicable. This way, the possibility that the PI or study staff inadvertently sees the Vascepa bottle is minimized. Subjects will be reminded not to disclose their group status to study staff other than the RA assigning the group.

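### The contraceptive methods offered to women on Vascepa include hormonal ones, some of which Table 2 excludes at entry

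*Combined protocol and SAP*

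**What the plan says.** The contraception request appears once, in C.4 under Visit # 2: "For subjects randomized to Vascepa, women who can become pregnant during the study will be asked to use a contraceptive method". The same sentence gives the methods and the period: "contraceptive method (i.e., hormone, intrauterine device, barrier, or abstinence) during the study and six months after the final visit". Control subjects are not asked.

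Table 2, part B, has a medication exclusion that begins: "Current use of insulin, cyclophosphamide, estrogen, fibrates, niacin, hormone replacement therapy, testosterone, oral contraceptives". It ends with a catch-all for other systemic steroids. Part B also excludes pregnancy and lactation.

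C.1 says of the criteria: "Complete list of inclusion and exclusion criteria is provided in Table 2". Agreement to contraception is not in that list, although another undertaking about behaviour is: "Willingness to abstain from fish oil, EPA, over the counter niacin, and other omega-3 fatty acid supplements during the study period (12 weeks)". At Visit # 1, after the PI has explained the study, the subject signs: "he/she will sign the informed consent prior to the beginning of the screening process". The consent form itself is not part of the text available.

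**The concern.** The entry criteria and the instruction after randomization treat the same drug class differently. Oral contraceptives and estrogen keep a person out of the trial if she already takes them. The contraception request then offers hormones, without qualification, as one acceptable way to comply.

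Two things are at stake, both small. The first is comparability: the request goes to the drug arm only, so any hormonal product started because of it would be started in that arm only. The second is clarity for staff: the plan does not tell them which hormonal methods, if any, are acceptable. A lesser matter is that the agreement is not among the listed criteria, so it is worth checking that it is obtained before allocation.

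**Working it through.** The plan gives no figure on this point, so there is nothing to reproduce. The check is a comparison of sections, followed by a rough count.

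**1. Can such women enter?** Yes. Table 2 admits ages 30 to 75, and C.4 provides a pregnancy test at Visit # 2 for pre-menopausal women who have not been surgically sterilized.

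**2. Each method in C.4 against Table 2, part B.**
- Intrauterine device (as a device), barrier and abstinence: no conflict.
- Hormonal, oral contraceptive: a named exclusion at entry.
- Hormonal, other product containing estrogen: estrogen is a named exclusion at entry.
- Hormonal, non-oral progestin-only: not named. Whether the systemic-steroid catch-all reaches it is unclear.

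The overlap is therefore real but partial, and every woman who is asked has compatible choices.

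**3. Is a criterion breached?** No. The exclusion is worded as current use and is applied at entry. But because current users have been screened out, an eligible woman who complies by taking an oral contraceptive or estrogen product must be a new starter.

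**4. When would the start fall?** The precaution covers 12 weeks of study plus six months (about 26 weeks): 12 + 26 = about 38 weeks. RHI and the biomarkers are measured at weeks 0 and 12, so a product started in the first 12 weeks lies between baseline and outcome. The last 26 weeks or so come after the final measurement and cannot affect the comparison.

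**5. How many women?** The documents do not say. As an assumption, take 0 to 4 of the 30 randomized as able to become pregnant, and 0 to 1/2 of those asked as choosing an excluded type of hormonal method.
- Expected in the EPA arm: 0 × 1/2 = 0 to 4 × 1/2 = 2.
- Expected to start such a product: 0 to 2 × 1/2 = 1, that is, up to 1 of 15 (about 7%) in that arm.

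These are expectations under assumed inputs, not limits. C.3 blocks on gender and ethnicity, not on childbearing potential, so all 4 could fall in the EPA arm.

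**The case against.** The strongest reply is that nothing here is contradictory. Table 2 governs entry and does not forbid starting a method later; three of the four listed methods raise no question, and few women are involved. All of this stands. It makes the point a clarification, but it does not explain why a class kept out at entry is offered afterwards in one arm.

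A reader might go further and infer that women receive Vascepa without ever having agreed to contraception. The documents do not support that. The consent form has not been seen and may contain the undertaking. The PI explains the protocol before signature, so a woman could learn of the request and decline then. C.4 does not say who makes the request or when, and its position next to the pregnancy test allows it to be read as a conditional instruction given before allocation. Visit # 3 repeats the Visit # 2 procedures, which on its face includes the pregnancy test. What is established is only that the criterion is absent from Table 2.

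A reader might also infer that controls should be asked too. Limiting the need for contraception to the drug arm is reasonable.

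**Conclusion.** The concern holds as a minor inconsistency. C.4 offers hormonal contraception without qualification, although Table 2 excludes current users of oral contraceptives and estrogen, and the request reaches the EPA arm only. It rests on the wording of two sections and on no calculation. The number of women is unknown and probably small; the range in the working is assumed.

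It would be tempting to call this a bias in the RHI or biomarker comparison. The documents do not support that: they do not say why these drugs are excluded and give no effect of them on the outcomes, so no direction or size can be stated. Power and precision are not in question.

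**What to change.** In C.4, Visit # 2, replace the hormonal option with methods that agree with Table 2: an intrauterine device, a barrier method or abstinence, or a specific hormonal method that the exclusion list does not cover, stated by name.

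As a small addition, first check the consent form. If it does not already cover the matter, have the PI confirm with every woman of childbearing potential, at consent or at the Visit # 2 pregnancy test and in any case before randomization, that she agrees to use one of these methods if allocated to Vascepa. Asking all such women beforehand tells the PI nothing about allocation. It therefore fits the C.6 arrangement in which the RA shares the assignment only "once all activities of study visit # 2 have been completed and PI and other staff have left the CCI".

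The cost is a few words in C.4 and perhaps one line in the consent form. An occasional woman will be screened out or will have fewer methods to choose from. I would not add rules for withholding or returning drug; how strictly to enforce a precaution is for the investigator and the IRB.

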## **C.3. Randomization Scheme**

Randomization will occur during the second study visit at the CCI for those who meet eligibility criteria. In this pilot study, 30 subjects will be randomized with equal probability to EPA intervention (n=15) or no EPA (no drug) (n=15) stratified according to gender. Permuted blocks (block size of 2) will be used to achieve groups of equal size. We will create blocks within each gender and each ethnicity (Caucasian, African- American, and others) to assure balance distribution of gender and ethnicity between the two groups.

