### **C.6. Assessment of Digital Pulse Amplitude**

Study subjects will be asked to refrain from caffeine-containing beverages or tobacco consumption 12 hours prior to the measurement of endothelial function. Digital pulse amplitude will be measured in the fasting state (as outlined above) with a fingertip peripheral arterial tonometry (PAT) device (Endo-PAT2000, Itamar Medical, Caesarea, Israel) in a supine position after a minimum of 20 minute rest in a quiet room with controlled temperature (20-23 degree Celsius). Details on digital pulse amplitude measurements have been published elsewhere. Briefly, the PAT device contains a pneumatic plethysmograph, which applies a uniform pressure to the surface of the distal index finger, thereby allowing measurement of pulse volume changes in the finger. Baseline pulse amplitude will be measured from each finger tip for about 5 minutes. The arterial flow will then be interrupted for 5 minutes with a cuff placed

on a proximal forearm with an occlusion pressure equal to the highest value of 200 mm Hg or the subject's systolic blood pressure plus 60 mm Hg. The contralateral arm (dominant arm) will serve as control. Lack of residual pulsatility will be monitored throughout the occlusion period. Pulse amplitude will be recorded electronically in the test and control fingers and analyzed by a computerized and automated algorithm that provides the average pulse amplitude for each 30-second interval after forearm cuff deflation up to 4 minutes (Itamar Medical). The change from the baseline measurement will be expressed as the reactive hyperemia index (RHI), which in part reflects vasodilator function of the digital microcirculation. Previous studies have demonstrated that RHI is to a large part dependent on nitric oxide bioavailability.

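### The blinded coordinator makes the monthly adverse-effect calls to subjects who know their arm, an avoidable route to unblinding that a stated block size of 2 widens

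*Combined protocol and SAP*

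**What the plan says.** - **Who is blinded.** C.4 (Visit # 2) makes the RA the unblinded person and continues: "Otherwise, PI, study coordinator, statistician, and other staff at the lab measuring biomarkers will all be blinded".
- **What subjects know.** The same paragraph says "Subjects randomized to Vascepa will know that they are taking the drug containing omega-3". Controls receive no drug, and the RA tells each subject the assignment.
- **Who calls.** Still in C.4: "Enrolled subjects will be contacted by telephone once a month by the coordinator to query about potential adverse effects". The call also serves as a reminder of the last visit.
- **Safeguards in C.6.** At visit 2, "an independent research assistant will share the assignment group with the study subject once all activities of study visit # 2 have been completed", after the PI and other staff have left. Then "during the third visit, the RA will see all study subjects before any blinded staff" and collects the bottle. Finally, "Subjects will be reminded not to disclose their group status to study staff other than the RA assigning the group".
- **Randomization.** C.3: "Permuted blocks (block size of 2) will be used to achieve groups of equal size". The section first describes stratification by gender, then blocks within gender and three ethnicity groups, so there are either two or six strata.
- **Other coordinator tasks.** The coordinator screens candidates by telephone (C.2) and telephones the visit 1 results that decide further eligibility (C.4, Visit # 1).

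**The concern.** The trial is open to subjects, so its blinding consists of staff not knowing assignments. C.6 sets out physical steps for the visits, but none of them applies to the telephone. There, a caller who is meant to stay blinded asks arm-aware subjects about adverse effects, a question that invites a treated subject to mention the capsules. Apart from the reminder, the plan gives no script and no step to follow after an accidental disclosure.

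Two features widen the consequence of a slip. With blocks of 2, one known arm determines another. And the person exposed to the slip also deals with later candidates, so an arm could become known before its holder is randomized, which is a loss of allocation concealment for that subject. The pilot's stated purpose is to estimate an effect size for a confirmatory trial, so the credibility of the estimate matters even though significance does not.

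**Working it through.** The plan gives no figure on this point. Its only design calculation (D.3: 80% power, 15 per arm, effect size 1.05) reproduces at 79.3% with a two-sided 5% t test, the level being assumed and 1.05 read as a standardized effect. It is not affected.

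**Inputs from the documents.** 30 subjects, 1:1, block size 2 (C.3); 12 weeks between visits 2 and 3 and monthly calls (C.4).

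**Assumed, because the documents do not say.** Leak probability per call; calls at weeks 4 and 8; uniform accrual over 6, 12 or 24 months; 50/50 gender and 70/20/10 ethnicity.

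**1. Number of calls.** Two to three per subject before visit 3: 30 × 2 = 60 to 30 × 3 = 90.

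**2. What one slip reveals.** A 1:1 block of 2 has only the sequences AB and BA, so the block-mate's arm follows with probability 1. An odd last subject in a stratum has no block-mate. On average 0.90 (six strata) or 0.97 (gender only) further arms become certain per disclosure.

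**3. Arms known before the subject's own visit 3.** Let q be the leak probability per call, with two calls each. Own slips give 1 − (1 − q)². Adding a block-mate whose calls all come in time gives at most 1 − (1 − q)⁴. The simulated column allows for call timing and unpaired subjects, across both strata readings and all accrual times.

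| q | own slips | ceiling with block-mate | simulated, blocks of 2 |
|---|---|---|---|
| 2.5% | 4.9% | 9.6% | 8-9.5% |
| 5% | 9.8% | 18.5% | 15-18% |
| 10% | 19.0% | 34.4% | 29-33% |

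All are zero if nothing leaks, and zero by this route if the RA makes the calls.

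**4. Arms known before randomization.** As an extreme case, suppose every subject disclosed at a first call 4 weeks after randomization. Entries are for accrual over 6 / 12 / 24 months. The mixed-block guesser is allowed to know that sizes are 2 or 4 with equal chance.

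| | certain in advance | best-guess success |
|---|---|---|
| Six strata, blocks of 2 | 12 / 23 / 32% | 56.0 / 61.4 / 65.9% |
| Six strata, mixed 2 and 4 | 3 / 5 / 7% | 56.8 / 61.2 / 64.5% |
| Gender only, blocks of 2 | 4 / 14 / 26% | 52.0 / 57.1 / 63.2% |
| Gender only, mixed 2 and 4 | 2 / 5 / 7% | 53.4 / 58.7 / 63.5% |

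At 10% disclosure, advance certainty with blocks of 2 falls to 1.2-3.2% (six strata) or 0.4-2.6% (gender only). Instant knowledge of every earlier arm would give 0.902/2 = 45% or 0.967/2 = 48%, which is an upper bound only. Mixed blocks remove most of the certainty, but the best-guess rate moves by less than 2 points, in either direction.

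**5. What mixed blocks cost in balance.** With gender strata and blocks of 2, the two gender counts are both even about half the time, which forces 15/15. Otherwise one unpaired subject remains in each gender, and they fall in opposite arms half the time: 0.5 + 0.5 × 0.5 = 75%. Mixed blocks lower this to about 64%. With six strata the figures are about 45% and 39%. The loss of precision is slight: for a 17/13 split the standard error ratio is √[(1/17 + 1/13)/(2/15)] = 1.009.

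**The case against.** **The reminder already covers the calls.** It is worded for all study staff other than the RA and is not limited to visits. This stands: the calls are not unprotected. They rest on subjects' restraint alone.

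**Visit 3 is a closer route.** A reader might infer that the calls are the one gap in an otherwise protected design. The documents do not support that. Having the RA see subjects first is meant to keep the bottle out of sight; it does not stop a subject from speaking. The PI, who measures RHI, then spends at least a 20-minute rest and the test session with someone who knows the arm, under the same reminder. Moving the calls leaves that route open.

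**No direct path to an outcome.** The coordinator measures nothing named in D.1 or D.2. The PI measures RHI, and the recordings are "analyzed by a computerized and automated algorithm". Laboratory and analysis staff are blinded, and eligibility turns on measured RHI and triglycerides. This also stands: knowledge from a call would have to reach the PI, or affect enrolment or scheduling, before it could matter.

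**Reading off a block-mate needs stratum and order.** The documents do not say that the coordinator has them. It is plausible for someone who screens candidates and telephones results, but it is an inference.

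**Blocks of 2 have a purpose.** C.3 chooses them for equal group sizes, and mixed blocks give up some of that without making guesses less successful. For this reason the block change is optional.

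**Conclusion.** The point holds as a modest one. The plan assigns a member of staff it calls blinded to question arm-aware subjects every month, with a request for silence as the only barrier, although an unblinded member of staff is available. The stated block size of 2 nearly doubles what a slip can reveal and can expose an arm in advance.

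The block-of-2 deduction is exact. Everything beyond it depends on disclosure rates, call timing, accrual and subject mix that the documents do not give. Over assumed leak rates of 2.5% to 10% per call, 8% to 33% of subjects would have an arm known before their own visit 3, against 5% to 19% from own slips alone.

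A reader might go further and conclude that the blind fails or that RHI will be biased. Neither follows: no disclosure is shown, and the link from the calls to RHI is indirect. Treat this as an inexpensive improvement to consider.

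**What to change.** **Main change (C.4).** Have the already unblinded RA, in place of the coordinator, make the monthly adverse-effect calls and visit reminders. This is one sentence and about 60-90 short calls moved between existing staff. The downside is that adverse-effect queries would no longer come from nominally blinded staff; adverse effects are not an outcome in D.1 or D.2.

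**Optional change (C.3).** Replace the fixed block of 2 with randomly varying small blocks. The protocol would say only that sizes vary and are concealed, and the sizes (for example 2 and 4) would sit in a restricted document kept from enrolling and assessing staff. This removes most certainty about a block-mate's arm. It does not make guesses less successful, and it lowers the chance of an exact 15/15 split as shown above. Once the calls are moved, it protects only against slips elsewhere, such as at visit 3.
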